9.3 Clinical Laboratory Evaluations

Laboratory data for Chemistry, Hematology, Urinalysis, and Blood lipids will include the following analytes:

- Chemistry: alkaline phosphatase, alanine aminotransferase (ALT), aspartate
 aminotransferase (AST), bicarbonate, blood urea nitrogen, calcium, chloride, cholesterol,
 creatinine phosphokinase, creatinine, glucose, lactate dehydrogenase, magnesium,
 phosphorus, potassium, sodium, total and direct bilirubin, uric acid
- Hematology: basophils, eosinophils, hematocrit, hemoglobin, white blood cell count, lymphocytes, monocytes, neutrophils, platelet count, red blood cell count, mean corpuscular hemoglobin, mean corpuscular hemoglobin concentration
- Urinalysis: bilirubin, blood, glucose, ketones, leukocyte esterase, pH, protein, specific gravity, urinary creatinine and uric acid
- **Blood Lipids**: total cholesterol, triglycerides (TG), high-density lipoprotein (HDL) and low-density lipoprotein (LDL)

Laboratory data will be summarized separately for each category by visit for the safety population. Descriptive summaries of actual values and changes from Baseline will be presented by study visit.

Laboratory values will be displayed in the data listings and those that are outside the normal range will be flagged as normal, high or low, along with corresponding normal ranges (if available).

Pregnancy test results will be listed separately.

9.4 Vital Signs

Descriptive summaries of actual values and changes from baseline to each scheduled visit will be calculated for vital signs including heart rate (HR), respiratory rate (RR), temperature (Temp), systolic and diastolic blood pressure.

A listing of all vital signs will be provided.

9.5 Physical Examination

All physical examination results will be listed only.

9.6 Concomitant Medications

All medications will be coded using the World Health Organization Drug Dictionary (WHO-DD) (Version March 2015 or most recent version) and summarized by ATC Level 3 term and preferred term on the safety population.

9.7 Exposure to Treatment

The number of days of RELiZORB use for the overall treatment period, between Visits 2 and 3 (including Visit 2), between Visits 3 and 4 (including Visit 3), and between Visits 4 and 5 (including Visit 4 and 5) will be calculated. The average weekly number of days of RELiZORB use between these visits will be determined by first taking the number of days between Visits (date of last Visit – date of current visit +1) and dividing by 7. This will give us the number of weeks between Visits. Next, the number of days of RELiZORB use will be divided by the number of weeks between Visits to provide the average weekly RELiZORB use between Visits. Average weekly number of days of RELiZORB use for the overall treatment period will be calculated in the same manner.

Average volume of formula administered (mL/day) for the overall treatment period via RELiZORB is defined as the total volume of formula administered via RELiZORB across study / Number of days a RELiZORB administration occurred. Average volume between Visits 2 and 3 (including Visit 2), between Visits 3 and 4 (including Visit 3), and between Visits 4 and 5 (including Visit 4 and 5) will be calculated in the same manner as average volume for total study period except that the total volume of formula administered via RELiZORB / the number of days a RELiZORB administrations occurred between visits will be used.

Study treatment adherence will be calculated for each subject and summarized descriptively. Adherence will be defined as the number of days the RELiZORB is used divided by the number of days inclusive from Visit 2 through Visit 5, multiplied by 100. Adherence between visits will be summarized and defined as the number of days the RELiZORB is used between Visits (as defined in the first paragraph) divided by the number of days between Visits (Visits 2 and 3,

Visits 3 and 4, Visits 4 and 5), multiplied by 100.

The analysis will be completed using the safety population.

All RELiZORB usage information will be included in a subject listing.

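### SAP 9.7: the between-visit weekly-use denominator is one day longer than the numerator window for Visits 2–3 and 3–4, so weekly use there is understated by about 3%

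*SAP*

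**What the plan says.** All of this is in SAP 9.7 (Exposure to Treatment).

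- **Days of use, first two intervals.** The windows are "between Visits 2 and 3 (including Visit 2), between Visits 3 and 4 (including Visit 3"), so each contains its opening visit and not its closing visit.
- **Days of use, last interval.** The window is "between Visits 4 and 5 (including Visit 4 and 5) will be calculated", so it contains both visits. SAP 9.8 uses the same three windows for device problems. The split therefore looks deliberate: each visit day belongs to exactly one interval.
- **Weeks in the interval.** One rule serves every interval: "taking the number of days between Visits (date of last Visit – date of current visit +1) and dividing by 7". I read "date of last Visit – date of current visit +1" as later date minus earlier date plus 1, which counts both end visits.
- **Weekly use.** "the number of days of RELiZORB use will be divided by the number of weeks between Visits".
- **Between-visit adherence.** The numerator is "the number of days the RELiZORB is used between Visits (as defined in the first paragraph"); this is "divided by the number of days between Visits (Visits 2 and 3", and so on for the other two intervals). The cross-reference to the first paragraph is attached to the days of use. No separate formula is given for the denominator.
- **Overall adherence.** The denominator is the inclusive day count from Visit 2 through Visit 5.

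**The concern.** A rate needs a numerator and a denominator that cover the same days. In the first two intervals the denominator covers one day, the closing visit, on which use is not counted in that interval. That day reappears as the opening day of the next interval, so the dates of Visits 3 and 4 each enter two denominators but only one numerator.

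The between-visit rows of the RELiZORB Administration table (14.1.4 in SAP 12.1) would then understate weekly use in two of three intervals and would not reconcile with the overall row. Because the mismatch applies to some intervals and not others, a reader comparing intervals would be comparing figures built on different rules.

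**Working it through.** The SAP states no exposure figure, so there is nothing to reproduce; the check is day counting from its own definitions.

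**Inputs**
- Nominal visit days 0, 30, 60 and 90 (SAP 8.1), so L = 30 days in each interval.
- Visit window ±4 days (note to SAP Table 1). Both ends can move, so L runs from 30 − 8 = 22 to 30 + 8 = 38.
- Windows and the +1 rule from SAP 9.7.
- Enrolment requires formula use at least four to five times per week (Protocol 4.4.1), so daily use is the ceiling and not the typical case.

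**Formulas**
- Largest possible numerator: L for Visits 2–3 and 3–4; L + 1 for Visits 4–5.
- Denominator under the +1 rule: L + 1 for all three.
- Weekly use = days of use ÷ (denominator ÷ 7). Adherence = 100 × days of use ÷ denominator.

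**Daily use on the nominal schedule, with use possible on the Visit 5 date**

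| Period | Days of use | Denominator | Weekly use | Adherence, with +1 | Adherence, without +1 |
|---|---|---|---|---|---|
| Visits 2–3 | 30 | 31 | 6.77 | 96.8% | 30/30 = 100% |
| Visits 3–4 | 30 | 31 | 6.77 | 96.8% | 30/30 = 100% |
| Visits 4–5 | 31 | 31 | 7.00 | 100% | 31/30 = 103.3% |
| Overall | 91 | 91 | 7.00 | 100% | not applicable (defined as inclusive) |

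The interval numerators sum to 30 + 30 + 31 = 91, the overall count. The denominators sum to 3 × 31 = 93; the two extra days are Visits 3 and 4.

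**Across the visit windows.** The ceiling in the first two intervals runs from 22/23 (6.70 days/week, 95.7%) to 38/39 (6.82 days/week, 97.4%). It never reaches 7.

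**Less than daily use.** Any true rate in those intervals is multiplied by L/(L+1). At L = 30, 5 days/week becomes 5 × 30/31 = 4.84, a loss of 0.16.

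**If no use-day can fall on the Visit 5 date.** Visits 4–5 then hold at most 30 days of use, and 30/31 = 96.8% (6.77 days/week) equals the ceiling of the other two intervals, so no rise appears on the nominal schedule. The overall ceiling becomes 90/91 = 98.9%.

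**With matched denominators.** These are 30 + 30 + 31 = 91 if the Visit 5 date counts, or 30 + 30 + 30 = 90 if it is dropped from both sides. Daily use then gives 7.00 days/week and 100% in every interval and overall.

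**The case against.** Four points can be made on the other side.

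1. **Trend.** A reader might infer that identical behaviour will show as rising use in the last interval. The documents do not support this as a certainty, because it needs a use-day on the Visit 5 date. Protocol 2.3 describes tube feeding as usually nocturnal, and Protocol 4.3 has subjects bring all used and unused devices to the Day 90 visit. If an overnight feed is dated by its start, the last one may fall on Day 89. Against that, Protocol 4.9.10 gives the treatment period as Days 0 to 90, and a feed could be dated by its end. The log's convention is not stated. This objection stands: the rise is conditional. It also means that removing the +1 from the first two intervals alone could produce an apparent fall, with ceilings of 100%, 100% and 30/31 = 96.8%.

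2. **Adherence.** A reader might also infer that between-visit adherence can never reach 100% in the first two intervals. The +1 is explicit only for weekly use, so the adherence denominator could be the plain date difference, and the flat statement does not hold. The text still fails, because the plain difference allows 103.3% in Visits 4–5. Neither rule fits all three windows.

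3. **Ceilings rarely bind.** Many subjects may feed four or five times a week, so few would meet a 7-day or 100% ceiling. That is fair, but the proportional understatement applies at every level of use.

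4. **Consequence.** Exposure is descriptive. The Per Protocol definition (SAP 5) has no numerical adherence threshold, and overall adherence has its own inclusive denominator. This stands and limits the importance of the point.

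**Conclusion.** The weekly-use rule is wrong as written for Visits 2–3 and 3–4. It understates use by the factor L/(L+1), about 3% at 30 days, or at most 0.23 days/week (7.00 − 6.77) on the nominal schedule. This follows directly from the stated windows and formula.

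Between-visit adherence is ambiguous and faulty on either reading: a ceiling of 96.8% in the first two intervals with the +1, or up to 103.3% in the last without it. The second figure assumes that a use-day can be logged on the Visit 5 date, as does any spurious rise in the last interval.

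The point is minor. It affects descriptive interval summaries only and touches no efficacy test or population definition. The mismatch does not carry into the overall figure; only the open question about the Visit 5 date bears on that.

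**What to change.** - Define each interval's denominator as the number of calendar days in its own numerator window: later date minus earlier date for Visits 2–3 and 3–4; the same plus 1 for Visits 4–5 and for the overall period, where the SAP counts Visit 5.
- Say explicitly that these denominators apply to both weekly use and adherence.
- State how the usage log dates an overnight feed, and confirm whether a use-day can fall on the Visit 5 date. If it cannot, remove that date from both the numerator window and the denominator for Visits 4–5 and overall.

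The cost is a sentence or two in SAP 9.7, a small programming change and one check of the log convention. No new data are needed and trial conduct does not change.

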9.8 Equipment Adverse Experience (RELiZORB Usage)

The number of subjects who experienced at least one operational problem with the device along with the reported problem will be summarized for the overall treatment period including for the following periods: between Visits 2 and 3 (including Visit 2), between Visits 3 and 4 (including Visit 3), and between Visits 4 and 5 (including Visit 4 and 5). The number of times each problem was reported will also be summarized. Only problems due to the investigational device will be summarized.

A listing including the details for the equipment adverse experience will be included.

10. CHANGES FROM PLANNED ANALYSIS

The following items were changed from the planned analysis specified in the protocol:

Protocol Version 2.0	Updated Planned Statistical Analysis Changes From the Protocol	Justification For Change
7.4.2 Safety Population The safety population includes all subjects who received at least one RELiZORB exposure. For subjects who withdraw from the study, every effort will be made to retrieve safety information.	7.4.2 Intent to Treat The ITT population, includes all subjects who received at least one RELiZORB exposure. This population is the same as safety and will be referenced as ITT for efficacy analysis.	To clarify study populations for safety and for efficacy analysis.
Section 7.5 Procedures for Handling Missing, Unused and Spurious Data All available safety and tolerability data will be presented in data listings and tabulations. No data imputation will be applied for missing values.	Section 6.2 Handling of Missing Data Available subject data will be used in the statistical analysis. For the MMRM analysis, subjects who lack all post-baseline measures, the baseline efficacy outcome will be imputed for all post-baseline responses (i.e., no change from baseline).	There really is no change for subjects who are missing post-baseline data.

Section 7.7 Safety Analysis (paragraph 3) For the comparison between GI symptoms recorded during the run in period and the treatment period, the following analyses will be performed: No. of days where any symptom occurred; No. of days each symptom occurred; No. of days when severity was 1, 2 or 3 Symptom duration of <15min, 15-30min, 31-60min or >60min.	Removal of GI symptoms analysis: No. of days when severity was 1, 2 or 3 Symptom duration Any GI comparisons using ANOVA	Based on the fact that the GI symptom diary is a self-reporting diary, where collection of input like severity of symptoms is not validated, analysis is descriptive.
Section 7.8 Efficacy Analysis Comparison of these values during the run in and treatment periods will be performed using analysis of variance (ANOVA).	Analysis updated to a repeated measures analysis to compare mean values at baseline to Days 30, 60, and 90.	The MMRM statistical model in the SAP is an extension of the proposed model and accommodates random and fixed effects in the context of repeated measures.

12. TABLES, LISTINGS, AND FIGURES

All listings, tables, and figures will have a header showing the sponsor company name [Alcresta Therapeutics, Inc.], protocol number, output version, and a footer showing the filename and path, date of output generation, and date of data cut. All tables and figures will have a "SOURCE: Listing(s) xxxx" line that indicates which data listing contains the underlying data.

Page 24 of 87

12.1 Planned Table Descriptions

The following are planned summary tables for protocol 0000498:

Table Number	Population	Title	Listing Reference
14.1.1	All Subjects	Subject Disposition	16.2.1.1, 16.2.1.2
14.1.2	All Enrolled Subjects	Protocol Deviations/Violations	16.2.2.1
14.1.3	Safety	Demographics and Baseline Characteristics	16.2.3.1
14.1.4	Safety	RELiZORB Administration	16.2.4.1, 16.2.4.2, 16.2.4.3
14.1.5	Safety	Equipment Adverse Experience	16.2.4.4
14.2.1.1a	ITT	Changes over Time in Tissue (Erythrocyte Membrane) Composition (%) for EPA+DHA (omega-3 index): Primary Efficacy Endpoint	16.2.5.1.1
14.2.1.1b	Per Protocol	Changes over Time in Tissue (Erythrocyte Membrane) Composition (%) for EPA+DHA (omega-3 index)	16.2.5.1.1
14.2.1.1c	ITT	Changes over Time in Tissue (Erythrocyte Membrane) Composition (%) for EPA+DHA (omega-3 index) by Age Subgroup	16.2.5.1.1
14.2.1.1d	ITT	Changes over Time in Tissue (Erythrocyte Membrane) Composition (%) for EPA+DHA (omega-3 index) by CFRD Subgroup	16.2.5.1.1
14.2.1.2	ITT	Changes over Time in Tissue (Erythrocyte Membrane) Composition (%) for EPA and DHA	16.2.5.1.1
14.2.1.3a	ITT	Changes over Time in Tissue (Erythrocyte Membrane) Composition (%) Ratio of Omega-6 to Omega-3 Fatty Acids	16.2.5.4.1
14.2.1.3b	ITT	Changes over Time in Tissue (Erythrocyte Membrane) Composition (%) Ratio of Omega-6 to Omega-3 Fatty Acids by Age Subgroup	16.2.5.4.1
14.2.1.3c	ITT	Changes over Time in Tissue (Erythrocyte Membrane) Composition (%) Ratio of Omega-6 to Omega-3 Fatty Acids by CFRD Subgroup	16.2.5.4.1
14.2.1.4a	ITT	Changes over Time in Plasma Fatty Acid Concentration (µg/mL) of Total EPA+DHA	16.2.5.2.1
14.2.1.4b	ITT	Changes over Time in Plasma Fatty Acid Concentration (µg/mL) of Total EPA+DHA by Age Subgroup	16.2.5.2.1

Table Number	Population	Title	Listing Reference
14.2.1.4c	ITT	Changes over Time in Plasma Fatty Acid Concentration (µg/mL) of Total EPA+DHA by CFRD Subgroup	16.2.5.2.1
14.2.1.5	ITT	Changes over Time in Plasma Fatty Acid Concentration (µg/mL) of Total EPA and Total DHA	16.2.5.2.1
14.2.1.6a	ITT	Changes over Time in Plasma Composition (%) Ratio of Omega-6 to Omega-3 Fatty Acids	16.2.5.3.1
14.2.1.6b	ITT	Changes over Time in Plasma Composition (%) Ratio of Omega-6 to Omega-3 Fatty Acids by Age Subgroup	16.2.5.3.1
14.2.1.6c	ITT	Changes over Time in Plasma Composition (%) Ratio of Omega-6 to Omega-3 Fatty Acids by CFRD Subgroup	16.2.5.3.1
14.2.1.7	ITT	Changes over Time in Serum Protein Concentrations (Total Protein, Prealbumin, Albumin, and Transferrin)	16.2.5.6.1
14.2.1.8	ITT	Changes over Time in Urinary Leukotriene E4	16.2.5.7.1
14.2.1.9a	ITT	Changes over Time in Plasma Concentrations of Fat Soluble Vitamins (A, D, and E)	16.2.5.5.1
14.2.1.9b	ITT	Changes over Time in Plasma Concentrations of Fat Soluble Vitamins (A, D, and E) by Age Subgroup	16.2.5.5.1
14.2.1.10	ITT	Weight and Body Mass Index (BMI) Z-scores by Age Subgroup and Comparison to Historic Z-score	16.2.5.10.1
14.2.1.11	ITT	Changes over Time in Weight Gain Velocity (g/kg/90 days) Compared to Historical by Age Subgroup	16.2.5.9.1
14.3.1.1	Safety	Summary of Adverse Events	16.2.6.1, 16.2.6.2, 16.2.6.3, 16.2.6.5
14.3.1.2	Safety	Adverse Events by System Organ Class and Preferred Term	16.2.6.1
14.3.2.1	Safety	Unanticipated Adverse Device Effects by System Organ Class and Preferred Term	16.2.6.3
14.3.2.2	Safety	Unanticipated Adverse Device Effects by System Organ Class, Preferred Term, and Relationship	16.2.6.3
14.3.2.3	Safety	Unanticipated Adverse Device Effects by System Organ Class, Preferred Term, and Severity	16.2.6.3

Table Number	Population	Title	Listing Reference
14.3.3.1	Safety	Gastrointestinal Symptom Diary: Frequency and Incidence – Overall and by Symptom	16.2.7.1
14.3.4.1	Safety	Summary of Clinical Chemistry Measurements: Results and Change from Baseline	16.2.8.1
14.3.4.2	Safety	Summary of Hematology Measurements: Results and Change from Baseline	16.2.8.2
14.3.4.3	Safety	Summary of Numeric Urinalysis Measurements: Results and Change from Baseline	16.2.8.3
14.3.4.4	Safety	Summary of Blood Lipids: Results and Change from Baseline	16.2.8.4
14.3.5.1	Safety	Summary of Vital Sign Measurements: Results and Change from Baseline	16.2.9.1
14.3.6.1	Safety	Concomitant Medications	16.2.3.3

12.2 Planned Listing Descriptions

The following are planned data and patient data listings for protocol 0000498:

Listing Number	Population	Title	
16.2.1.1	All Subjects	Analysis Populations	
16.2.1.2	All Enrolled Subjects	Patient Disposition	
16.2.1.3	All Subjects	Inclusion and Exclusion Criteria	
16.2.2.1	All Subjects	Protocol Deviations/Violations	
16.2.3.1	All Subjects	Demographics and Baseline Characteristics	
16.2.3.2	All Subjects	Medical History	
16.2.3.3	All Subjects	Concomitant Medications	
16.2.4.1	Safety	Enteral Tube Feeding Pre-Baseline and Baseline before Start of RELiZORB	
16.2.4.2	Safety	RELiZORB Usage Log	
16.2.4.3	Safety	RELiZORB Administration and Study Treatment Adherence	
16.2.4.4	Safety	Equipment Adverse Experience	
16.2.5.1.1	ITT	Composition (%) of EPA, DHA and DHA plus EPA (%) in Erythrocyte Membranes Gas Chromatography/Mass Spectrophotometry (GCMS)	
16.2.5.1.2	Subjects Excluded from Per Protocol	Composition (%) of EPA, DHA and DHA plus EPA (%) in Erythrocyte Membranes Gas Chromatography/Mass Spectrophotometry (GCMS)	
16.2.5.2.1	ITT	Concentrations (µg/mL) of Total DHA, Total EPA, and Total EPA+DHA Ultra High Performance Liquid Chromatography (UHPLC)	
16.2.5.2.2	Subjects Excluded from Per Protocol	Concentrations (µg/mL) of Total DHA, Total EPA, and Total EPA+DHA Ultra High Performance Liquid Chromatography (UHPLC)	
16.2.5.3.1	ITT	Plasma Composition (%) Ratio of Omega-6 to Omega-3 Fatty Acids Gas Chromatography/Mass Spectrophotometry (GCMS)	
16.2.5.3.2	Subjects Excluded from Per Protocol	Plasma Composition (%) Ratio of Omega-6 to Omega-3 Fatty Acids Gas Chromatography/Mass Spectrophotometry (GCMS)	
16.2.5.4.1	ITT	Tissue (Erythrocyte Membrane) Composition (%)	

		Ratio of Omega-6 to Omega-3 Fatty Acids	
		Gas Chromatography/Mass Spectrophotometry (GCMS)	
16.2.5.4.2	Subjects Excluded	Tissue (Erythrocyte Membrane) Composition (%)	
	from Per Protocol	Ratio of Omega-6 to Omega-3 Fatty Acids	
	and all and a fine of the second and a second a second and a second an	Gas Chromatography/Mass Spectrophotometry	
		(GCMS)	
16.2.5.5.1	ITT	Plasma Concentrations of Fat Soluble Vitamins (A, D and E)	
16.2.5.5.2	Subjects Excluded	Plasma Concentrations of Fat Soluble Vitamins (A, D	
10.2.3.3.2	from Per Protocol	and E)	
16.2.5.6.1	ITT	Serum Protein Concentrations	
16.2.5.6.2	Subjects Excluded	Serum Protein Concentrations	
10.2.3.0.2	from Per Protocol	Serum Frotein Concentrations	
16.2.5.7.1	ITT	Urinary Leukotriene E ₄ (LTE4)	
16.2.5.7.2	Subjects Excluded	Urinary Leukotriene E ₄ (LTE4)	
	from Per Protocol		
16.2.5.8.1	ITT	Weight, Height, and Body Mass Index	
16.2.5.8.2	Subjects Excluded	Weight, Height, and Body Mass Index	
	from Per Protocol	and the Control of th	
16.2.5.9.1	ITT	Weight Gain Velocity	
16.2.5.9.2	Subjects Excluded	Weight Gain Velocity	
	from Per Protocol	,	
16.2.5.10.1	ITT	Weight and Body Mass Z-scores	
16.2.5.10.2	Subjects Excluded	Weight and Body Mass Z-scores	
	from Per Protocol		
16.2.6.1	All Enrolled Subjects	Adverse Events	
16.2.6.2	All Enrolled Subjects	Adverse Events Leading to Discontinuation of	
		Enteral Feeding	
16.2.6.3	All Enrolled Subjects	Unanticipated Adverse Device Effects	
16.2.6.4	All Enrolled Subjects	Unanticipated Adverse Device Effects Leading to	
	- T	Discontinuation of Enteral Feeding	
16.2.6.5	All Enrolled Subjects	Serious Adverse Events	
16.2.6.6	All Enrolled Subjects	Deaths	
16.2.7.1	All Enrolled Subjects	Gastrointestinal Symptom Diary	
16.2.8.1	All Enrolled Subjects	Clinical Laboratory Tests: Chemistry	
16.2.8.2	All Enrolled Subjects	Clinical Laboratory Tests: Hematology	
16.2.8.3	All Enrolled Subjects	Clinical Laboratory Tests: Urinalysis	
16.2.8.4	All Enrolled Subjects	Clinical Laboratory Tests: Blood Lipids	
16.2.9.1	All Enrolled Subjects	Vital Signs	
16.2.9.2	All Enrolled Subjects	Physical Examination	
16.2.10.1 All Enrolled Subjects		Telephone Contact Log	

12.3 Planned Figure Descriptions

The following are planned summary figures for protocol 0000498:

Figure Number	Population	Title	Reference Table
14.2.1.1	Per Protocol	Boxplot of Erythrocyte Membrane Fatty Acid Composition (%) for EPA, DHA and DHA plus EPA (%)	14.2.1.1a
14.2.1.2	Per Protocol	Boxplot of Plasma Fatty Acid Concentration (μg/mL) for Total EPA, Total DHA, and Total EPA+DHA (μg/mL)	14.2.2.1b
14.2.1.12	Per-Protocol	Boxplot of Weight and Body Mass Index (BMI) Z-scores	14.2.1.10
14.2.1.13	Per-Protocol	Boxplot of Weight Gain Velocity (g/kg/30 days)	14.2.1.11
